# 3.3 Gynecological/Obstetrical and PCOS History

A detailed gynecological/obstetrical and PCOS history will be collected either during the Washout Period (if applicable) or during the Screening Period for those who do not require washout, and will include the following:

- History of PCOS, including year of diagnosis and PCOS symptoms
- History of endometriosis, ovarian cysts, endometrial polyps, or other relevant gynecological conditions
- History of gynecological surgeries and gynecological diagnostic procedures
- History of bleeding, including average cycle length and average number of days with bleeding/cycle over the last 6 months and typical intensity of menstrual periods
- History of irregular bleeding or prolonged bleeding

No use or disclosure outside AbbVie is permitted without prior written authorization from AbbVie.

- Prior hormonal medications, including those taken for treatment of PCOS or other gynecological conditions
- Prior use of nonhormonal medications for the treatment of PCOS including pain medication, including dates of use for 12 months prior to either Washout (if applicable) or Screening
- History of sexually transmitted infections
- Obstetrical history
- Pregnancy history including:
  - Total number of pregnancies
  - Number of live births
  - Number of abortions (including elective, therapeutic, and spontaneous abortions)
  - Delivery outcomes (specifically anomalies, including congenital malformations and chromosomal abnormalities).

The gynecological/obstetrical and PCOS history will be reviewed and should be updated if needed prior to dosing on Baseline (randomization) and will serve as the Baseline for clinical assessment.

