8.3 Primary Efficacy Endpoint(s) and Analyses

8.3.1 Primary Efficacy Endpoint(s)

The primary efficacy endpoint is the proportion of menstrual cycle responders.

A subject is considered as a menstrual cycle responder if she has at least 2 normal menstrual cycles during the final 4 months of the Treatment Period. For subjects who complete the treatment period this will be Month 3 to Month 6; for subjects who prematurely discontinue at Month X, where X is greater than or equal 4, this will be Month (X – 3) to Month X; for subjects who prematurely discontinue at Month X, where X is less than 4, this will be Month 1 to Month X. A normal menstrual cycle will be defined as follows:

- a. Subject has menstrual bleeding (excluding spotting only) AND
- b. The length of the menstrual cycle is from 21 to 35 days. Menstrual cycle length is defined as the length of time from the first day of one menstrual bleeding episode to the day before the next menstrual bleeding episode (calculated by [first day of the next menstrual bleeding episode] minus [the first day of the referenced bleeding episode]).

A menstrual bleeding episode is defined with the following rules:

- a. A bleeding episode requires at least one of the following:
 - At least 2 consecutive days of bleeding, OR
 - At least 1 day of bleeding followed immediately by 1 day of spotting or 1 day of missing data then spotting or 1 day of missing data then bleeding, OR
 - At least 1 day of spotting followed immediately by 1 day of bleeding or 1 day of missing data then bleeding.
- b. Consecutive days of spotting only with no days of bleeding are not considered as an episode.
- c. If consecutive days of spotting are adjacent to a day with bleeding, then these consecutive days with spotting are counted as part of the same bleeding episode.
- d. One day of missing data between a spotting day and bleeding day or between 2 bleeding days qualifies as part of the same bleeding episode.

Examples are presented in [Table 1](#).

Table 1. Examples of Menstrual Bleeding Episodes

Example	Days									Menstrual Bleeding Episode (Yes/No)	Duration (days)
	1	2	3	4	5	6	7	8	9		
A	x	●	x	x	x	x	x	x	x	No	N/A
B	x	○	○	x	x	x	x	x	x	No	N/A
C	x	●	●	x	x	x	x	x	x	Yes	2
D	x	○	●	x	x	x	x	x	x	Yes	2
E	x	●		●	x	x	x	x	x	Yes	3
F	x	●	x	●	x	x	x	x	x	No	N/A
G	x	○	●	●	x	x	x	x	x	Yes	3
H	x	○		●	x	x	x	x	x	Yes	3
I	x	○			●	x	x	x	x	No	N/A
J	x	○	●	●		●	○	x	x	Yes	6
K	x	○		○	○	●	●	○	x	Yes	5

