8.3.4 Additional Analyses of the Primary Efficacy Endpoint(s)

The following sensitivity analyses for the primary efficacy endpoint will be conducted:

1. The menstrual cycle response for subjects who prematurely discontinue the study drug at or before Month 4 will be considered as missing. Multiple imputation (MI) approach will be used for the primary endpoint. Details regarding MI are in Section 8.2.
2. Subjects who prematurely discontinue study drug during the Treatment Period due to "lack of efficacy" or adverse event (AE) will be considered as non-responders, while subjects who discontinue study drug during the Treatment Period due to other reasons will be categorized as responders/non-responders in the same manner as done in the primary analysis.
3. All subjects who prematurely discontinue the study drug at or before Month 4 will be considered as non-responders and the primary analysis will be repeated. Subjects who discontinue after Month 4 will be categorized as responders/non-responders in the same manner as done in the primary analysis.
4. The difference between each elagolix group and placebo group in proportion of menstrual cycle responders will be analyzed using contrasts within a logistic

regression model with the responder/non-responder categorization as the dependent variable, treatment as the main effect, and baseline FG score ($< 8, \geq 8$) and baseline normal/obese status ($\text{BMI} < 30, \geq 30$) as the covariates. The proportion of menstrual cycle responders, difference in proportions between each elagolix group and placebo, and odds ratio with corresponding 90% confidence interval and P value will be presented.

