8.5.3 Number of Menstrual Bleeding Episodes

Number of menstrual bleeding episodes during the Treatment Period will be analyzed using one-way ANCOVA with treatment group as the main effect, and baseline FG score ($< 8, \geq 8$) and normal/obese status ($\text{BMI} < 30, \geq 30$) as the covariates. Subjects who premature discontinue during the Treatment Period will be excluded from the analysis.

In addition, number of menstrual bleeding episodes per months of treatment will be analyzed using one-way ANCOVA with treatment group as the main effect, and baseline FG score ($< 8, \geq 8$) and normal/obese status ($\text{BMI} < 30, \geq 30$) as the covariates.

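### The normal-cycle rule in SAP 8.3.1 sets no limit on the length of a bleed, so a woman who bleeds or spots on most days can be scored as a menstrual cycle responder

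*SAP*

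**What the plan says.** A responder needs "at least 2 normal menstrual cycles during the final 4 months of the Treatment Period" (SAP 8.3.1; Protocol 7.3 uses the same threshold but does not define a normal cycle). SAP 8.3.1 sets two conditions for a normal cycle. The first is "Subject has menstrual bleeding (excluding spotting only) AND". The second is "The length of the menstrual cycle is from 21 to 35 days", with length "calculated by [first day of the next menstrual bleeding episode] minus [the first day of the referenced bleeding episode".

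The episode rules set a minimum of about two days, at least one of them bleeding rather than spotting. They set no maximum. Rule c begins "If consecutive days of spotting are adjacent to a day with bleeding" and assigns those spotting days to the episode, however many there are. Table 1 prints a duration for each qualifying example (2 to 6 days), but neither condition uses it.

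Complete response (SAP 8.5.1) takes over the same definition of a normal cycle. Days of bleeding appear in the SAP only as a baseline characteristic (7.1). On treatment, the diary endpoint outside the responder rules is a count of episodes (8.5.3). SAP 8.3.4 lists four sensitivity analyses, introduced by "The following sensitivity analyses for the primary efficacy endpoint will be conducted". Three change how discontinuation is handled and one changes the model; none changes the cycle rule.

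**The concern.** One of the protocol's clinical hypotheses is that elagolix restores normal menstrual cycles. The endpoint tests the spacing of onsets. It does not test whether the bleeds between those onsets are of ordinary length. A woman with short monthly bleeds and a woman with one clear day a month get the same score, on the primary endpoint and potentially on complete response. No planned analysis links response to the number of days bled, so the study report could not show whether its responders had cycles that a reader would call normal. With 20 women per active arm, a handful of such cases could matter.

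**Working it through.** **Inputs.** Cycle and episode rules: SAP 8.3.1. Study month of 28 days: Operations Manual 2.2, so the final four months are 4 × 28 = 112 days. Planning rates 10% and 50%, 30 placebo and 20 per elagolix group, two-sided 0.05: SAP 2.4. Analysis level 0.1: SAP 8.1.

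**The plan's own figure.** Power for 50% against 10% with 20 and 30 women is 88.9% by normal approximation, and by exact enumeration 89.7% (Pearson) or 86.2% (Fisher). The stated figure of at least 85% is reproduced and is not in dispute.

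**Check of the rule.** The episode rules were coded and run on Table 1. All 11 examples gave the printed yes/no and duration.

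**Implicit maximum.** An episode must end at least one day before the next onset. A bleed inside a normal cycle can therefore last up to 21 − 1 = 20 days or 35 − 1 = 34 days, depending on cycle length.

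**112-day diaries under the rule**

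| Diary | Days with bleeding or spotting | Normal cycles | Responder |
|---|---|---|---|
| 5 bleeding days every 28 | 4 × 5 = 20 | 3 | yes |
| 18 bleeding days on, 7 off | 4 × 18 + 12 = 84 | 4 | yes |
| 2 bleeding + 32 spotting days every 35 | 3 × 34 + 7 = 109 | 3 | yes |
| 20 on, 1 off, 20 on, 1 off, 70 on | 110 | 2 | yes |
| unbroken bleeding | 112 | 0 | no |
| unbroken spotting with 2 bleeding days | 112 | 0 | no |

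**Irregular bleeding.** Random runs were simulated with a mean of 5 to 40 days on and 2 to 5 off (an assumed model, 4,000 diaries per setting). Of the diaries with bleeding on most days, 6% to 37% were responders, depending on the setting. Most failed because their onsets were too close together or too far apart. Under an 8-day limit on the opening episode, used only to show that a limit discriminates, at most 4.5% of all simulated diaries in any setting were responders.

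**Sensitivity of a pairwise result.** Unstratified Pearson test, z = (p₁ − p₂) / √[p(1 − p)(1/20 + 1/30)], where p is the pooled proportion. At the planning rates, 10/20 against 3/30: p = 13/50 = 0.26, z = 0.40/0.1266 = 3.16, P = 0.002. The documents do not say how many women would be reclassified, so the rows below are assumed scenarios.

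| Elagolix | Placebo | P |
|---|---|---|
| 10/20 | 3/30 | 0.002 |
| 6/20 | 3/30 | 0.071 |
| 5/20 | 3/30 | 0.156 |
| 5/20 | 2/30 | 0.067 |
| 5/20 | 1/30 | 0.021 |

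Five women reclassified on elagolix and none on placebo takes the result past 0.1. One further woman reclassified on placebo brings it back below 0.1.

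**The case against.** The strongest reply is that the rule already screens out most disordered bleeding. Two onset intervals must fall within 21 to 35 days, continuous bleeding fails, and most simulated irregular patterns fail. An interval-based endpoint also matches the interval-based entry criterion, a cycle longer than 35 days (Protocol 5.1). This is a proof-of-concept study without Type I error control (SAP 10.0). The MBQ, adverse events and hemoglobin are all summarised, so an arm with heavy bleeding would not go unseen. These points stand, and they are reasons to leave the primary definition alone. They do not close the gap, because none of those summaries is tied to responder status.

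Three stronger readings are tempting, and the documents do not support them.

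- A reader might infer that prolonged bleeding on elagolix will inflate its response rate. No passage says that elagolix causes prolonged bleeding in these women, and long bleeds may occur on placebo too. The loss of significance at 5/20 against 3/30 comes from removing women from one arm only.
- A reader might take the Operations Manual 3.3 item "History of irregular bleeding or prolonged bleeding" as a study definition of abnormal bleeding. It is an entry in a list of history to record and sets no threshold.
- A reader might see the same fault in SAP 8.5.3, where "Number of menstrual bleeding episodes during the Treatment Period will be analyzed using one-way ANCOVA". That endpoint claims only to count episodes, and the 21-day floor in the primary rule already rejects onsets that come too often. Banding the count would not help. Exact 35-day cycles give only 4 episodes in 168 days for 7 of the 35 possible first-onset days (20%), although 168/35 = 4.8, and any band ignores spacing.

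**Conclusion.** The gap is real and its consequence is conditional. A woman who bleeds or spots on most days can be a responder, and under SAP 8.5.1 a complete responder, when enough of her onsets fall 21 to 35 days apart. In constructed diaries this happens with bleeding on up to 110 of 112 days. That part follows from the SAP's rules alone. The effect on the treatment comparison cannot be sized or signed, because neither the frequency of such women nor their balance between arms is given. The P values above show only that, with samples this small, reclassifying a few women in either arm could move a pairwise result across the 0.1 level. This is an inexpensive improvement to how the result can be interpreted. It does not show that the primary analysis is biased.

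**What to change.** Keep the primary definition.

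1. Add one sensitivity analysis to SAP 8.3.4 in which a normal cycle also requires the duration of its opening episode, derived as in Table 1, not to exceed a stated maximum. The sponsor should choose and justify that maximum and say whether spotting days count towards it, since the Table 1 durations include them. Apply the rule identically to all arms and to complete responders.
2. Fix the maximum in the SAP before anyone looks at responder data by arm. Protocol 7.1 leaves the sponsor unblinded throughout, so a value set later could look chosen from the data.
3. Report bleeding days, and bleeding-plus-spotting days, per 28 days by arm and by responder status.

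The daily e-Diary already records none, spotting or bleeding, so no new data are needed. The cost is SAP wording, a few derived variables and slightly more analysis work. The response rate may be lower under the stricter definition.

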8.3.2 Handling of Missing Data for the Primary Efficacy Endpoint(s)

The primary analysis will be based on observed cases only; missing data will not be imputed for the primary endpoint.

8.3.3 Primary Efficacy Analysis

The 5 primary null hypotheses for this study is that there are no differences in the proportion of women that are menstrual cycle responders between each elagolix dose group and placebo. Each null hypothesis will be tested against the alternative hypothesis that there is a difference between an elagolix group and placebo.

Each elagolix group will need to demonstrate a statistically significantly greater proportion of women that are menstrual cycle responders in order for that elagolix group to be considered more efficacious than placebo for the primary endpoint. That is, an elagolix group will be considered statistically more efficacious than placebo if the

two-sided p-value for the comparison of the proportion of menstrual cycle responders between that elagolix group and placebo is less than or equal to 0.1 and in favor of the elagolix group.

For the primary efficacy endpoint, the pairwise comparisons for the difference in proportion of menstrual cycle responders between each elagolix group and placebo will be analyzed using the Cochran-Mantel-Haenszel test (CMH) adjusted for FG score ($< 8, \geq 8$) and normal/obese status (BMI $< 30, \geq 30$) at Baseline. Additionally, the CMH-based 90% confidence interval for the difference in proportion of responders within each FG score ($< 8, \geq 8$) and normal/obese status (BMI $< 30, \geq 30$) at Baseline will be calculated based on normal approximation.

8.3.4 Additional Analyses of the Primary Efficacy Endpoint(s)

The following sensitivity analyses for the primary efficacy endpoint will be conducted:

1. The menstrual cycle response for subjects who prematurely discontinue the study drug at or before Month 4 will be considered as missing. Multiple imputation (MI) approach will be used for the primary endpoint. Details regarding MI are in Section 8.2.
2. Subjects who prematurely discontinue study drug during the Treatment Period due to "lack of efficacy" or adverse event (AE) will be considered as non-responders, while subjects who discontinue study drug during the Treatment Period due to other reasons will be categorized as responders/non-responders in the same manner as done in the primary analysis.
3. All subjects who prematurely discontinue the study drug at or before Month 4 will be considered as non-responders and the primary analysis will be repeated. Subjects who discontinue after Month 4 will be categorized as responders/non-responders in the same manner as done in the primary analysis.
4. The difference between each elagolix group and placebo group in proportion of menstrual cycle responders will be analyzed using contrasts within a logistic

regression model with the responder/non-responder categorization as the dependent variable, treatment as the main effect, and baseline FG score ($< 8, \geq 8$) and baseline normal/obese status ($\text{BMI} < 30, \geq 30$) as the covariates. The proportion of menstrual cycle responders, difference in proportions between each elagolix group and placebo, and odds ratio with corresponding 90% confidence interval and P value will be presented.

8.4 Secondary Efficacy Analyses

The key secondary endpoint is change from baseline in the area under the luteinizing hormone (LH) serum concentration-time curve over the 4 hours (area under the curve [AUC]) at Day 7. Serial blood samples for LH assay will be collected at Baseline and Weeks 1, 4, and 16 according to the following schedule: 0 hour, 0.5, 1, 1.5, 5, 2.5, 3, 3.5, and 4 hours. The AUC over the 4 hours will be calculated based on the linear trapezoidal rule.

The analysis for the key secondary endpoint will be based on a mixed-effects model with repeated measures (MMRM). If appropriate, the natural logarithmic transformation or other transformation may be employed for LH AUC. The MMRM analysis will include the fixed categorical effects of treatment, visit, treatment-by-visit interaction, baseline FG score ($< 8, \geq 8$), and baseline normal/obese status ($\text{BMI} < 30, \geq 30$), subject as a random effect, and the continuous fixed covariate of baseline LH AUC. Each elagolix dose group will be compared to the placebo group; the LS mean of treatment difference and associated 90% CI and p-value will be reported.

8.5 Additional Efficacy Analyses

8.5.1 Proportion of Complete Menstrual Cycle Responders

A subject is considered as a complete menstrual cycle responder if she has normal menstrual cycles by the beginning of Month 3 and maintained thereafter each month through Month 6 during the Treatment Period. Subjects who discontinued before

Month 6 during the Treatment Period will be considered as non-responders. A normal menstrual cycle has been defined in Section 8.3.1.

The pairwise comparisons for the difference in proportion of complete menstrual cycle responders between each elagolix group and placebo will be analyzed using the Cochran-Mantel-Haenszel test (CMH) adjusted for FG score ($< 8, \geq 8$) and normal/obese status ($\text{BMI} < 30, \geq 30$) at Baseline. Additionally, the CMH-based 90% confidence interval for the difference in proportion of complete menstrual cycle responders within each FG score ($< 8, \geq 8$) and normal/obese status ($\text{BMI} < 30, \geq 30$) at Baseline will be calculated based on normal approximation.

Same analysis will be conducted excluding subjects who premature discontinue during the Treatment Period.

8.5.2 LH, FSH, testosterone and other hormones

The changes from baseline to each scheduled assessment of the hormone parameters will be analyzed using a mixed-effects model with repeated measures (MMRM). If appropriate, the natural logarithmic transformation or other transformation may be employed for the hormone parameters. The MMRM analysis will include the fixed categorical effects of treatment, visit, treatment-by-visit interaction, baseline FG score ($< 8, \geq 8$), and baseline normal/obese status ($\text{BMI} < 30, \geq 30$), subject as a random effect, and the continuous fixed covariate of baseline hormone value.

8.5.3 Number of Menstrual Bleeding Episodes

Number of menstrual bleeding episodes during the Treatment Period will be analyzed using one-way ANCOVA with treatment group as the main effect, and baseline FG score ($< 8, \geq 8$) and normal/obese status ($\text{BMI} < 30, \geq 30$) as the covariates. Subjects who premature discontinue during the Treatment Period will be excluded from the analysis.

In addition, number of menstrual bleeding episodes per months of treatment will be analyzed using one-way ANCOVA with treatment group as the main effect, and baseline FG score ($< 8, \geq 8$) and normal/obese status ($\text{BMI} < 30, \geq 30$) as the covariates.

8.5.4 Ovulations

Determination of ovulation will be based on weekly serum progesterone level; a progesterone level ≥ 3 ng/mL will be used to indicate ovulation. One ovulation is defined as one weekly or more than one consecutive weekly serum progesterone level ≥ 3 ng/mL with the prior weekly serum progesterone level < 3 ng/mL or missing and the following weekly serum progesterone level < 3 ng/mL or missing.

Number of ovulations during the Treatment Period will be analyzed using one-way ANCOVA with treatment group as the main effect, and baseline FG score ($< 8, \geq 8$) and normal/obese status ($\text{BMI} < 30, \geq 30$) as the covariates. In addition, the proportion of subjects with at least 2 ovulations during the Treatment Period will be analyzed using the Cochran-Mantel-Haenszel test (CMH) adjusted for FG score ($< 8, \geq 8$) and normal/obese status ($\text{BMI} < 30, \geq 30$) at Baseline. Subjects who premature discontinue during the Treatment Period will be excluded from both analyses.

In addition, number of ovulations per months of treatment will be analyzed using one-way ANCOVA with treatment group as the main effect, and baseline FG score ($< 8, \geq 8$) and normal/obese status ($\text{BMI} < 30, \geq 30$) as the covariates.

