4.0 Analysis Populations

The following population sets will be used for the analyses.

The Full Analysis Set (FAS) consists of all randomly assigned subjects who have received at least one dose of study drug in this study. The data from the FAS will be presented by the treatment group assigned at the time of randomization, even if the subject does not

receive the correct treatment or does not follow the protocol until completion. The FAS will be used for all baseline and efficacy analyses.

The Safety Analysis Set consists of all subjects who received at least one dose of study drug. The data from the safety analysis set will be presented by the treatment actually received no matter what treatment group was assigned at the time of randomization. If a subject takes more than one treatment, the subject will be analyzed in the safety analysis set as taking the treatment to which she was randomized. All safety analyses will be performed based on the safety analysis set.

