8.0 Efficacy Analyses

8.1 General Considerations

All efficacy analyses will be conducted using the FAS. Unless otherwise specified, each elagolix dose group will be compared to placebo. All statistical tests will be conducted at an alpha level of 0.1 (two-sided). A test will be deemed significant if the P value rounded to three decimal places is less than or equal to 0.1 unless otherwise specified.

Unless otherwise specified, categorical data will be summarized by frequencies and percentages for each treatment group and overall; continuous data will be summarized by the mean, standard deviation, median, minimum, and maximum for each treatment group and overall. For the analyses of change from baseline, the within-group changes will be summarized with the mean, standard deviation, and the median; between-group differences will be summarized with the mean, standard error, P value, and the 90% CIs.

Baseline refers to the last non-missing value obtained prior to or on Study Day 1.

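### SAP 8.5.4 analyses the proportion with at least 2 ovulations only in subjects who do not discontinue early, and no companion analysis keeps the discontinuers

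*SAP*

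**What the plan says.** The general rule is the FAS. SAP 4.0 and Protocol 7.2 both state that "The FAS will be used for all baseline and efficacy analyses", and SAP 8.1 repeats that "All efficacy analyses will be conducted using the FAS". The FAS is every randomised subject with at least one dose, whether or not she completes.

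SAP 8.5.4 departs from this for two analyses: the ANCOVA of the ovulation count and the CMH test of the proportion with at least 2 ovulations. After describing them it says "Subjects who premature discontinue during the Treatment Period will be excluded from both analyses". It then adds one more analysis: "In addition, number of ovulations per months of treatment will be analyzed using one-way ANCOVA". No exclusion is attached to that one, but it concerns the count and not the proportion.

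Two other sections also drop discontinuers, each with a companion analysis:

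- SAP 8.5.1 (complete responders): subjects who stop before "Month 6 during the Treatment Period will be considered as non-responders". Only then does it add "Same analysis will be conducted excluding subjects who premature discontinue during the Treatment Period".
- SAP 8.5.3 (bleeding episodes): "Subjects who premature discontinue during the Treatment Period will be excluded from the analysis", followed by "In addition, number of menstrual bleeding episodes per months of treatment will be analyzed using one-way ANCOVA" with no exclusion stated.

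The multiple imputation in SAP 8.2 and the discontinuation rules in SAP 8.3.4 are written for the primary endpoint only.

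**The concern.** Completing treatment is a post-randomisation event. A comparison restricted to completers no longer rests on randomisation alone. If stopping is more frequent in one arm and is related to whether a woman ovulates, the completer difference can move away from the difference among all randomised subjects, in either direction. A woman who had 2 ovulations and then stopped has already met the endpoint as SAP 3.3 lists it, yet she is left out of both numerator and denominator.

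Improved ovulation is one of the four clinical hypotheses in Protocol 2.1, and this proportion is a listed endpoint tested against placebo at two-sided 0.1. As planned, a reader of the results could not see how far the proportion depends on leaving discontinuers out.

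**Working it through.** **1. Analyses that exclude discontinuers, and their companions**

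| Endpoint | Excluding analysis | Companion |
|---|---|---|
| Complete responders (8.5.1) | repeat CMH | CMH with discontinuers as non-responders |
| Bleeding episodes (8.5.3) | count ANCOVA | per-month ANCOVA, no exclusion stated |
| Number of ovulations (8.5.4) | count ANCOVA | per-month ANCOVA, no exclusion stated |
| At least 2 ovulations (8.5.4) | CMH | none |

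The gap is the last row. A mean rate per month does not give the share of women who reach 2.

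**2. Inputs**

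From the documents: 20 subjects per elagolix group and 30 on placebo (SAP 2.4); CMH stratified by FG score and BMI (8.5.4); two-sided 0.1 (8.1). The plan states no figure for this proportion, since its power statement concerns the primary endpoint. Every rate below is assumed.

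**3. Size when the all-subject rate is equal**

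Suppose 30% in each randomised arm reach 2 ovulations before stopping or finishing, so the true difference on that composite is 0. Let d1 and d0 be the shares stopping on elagolix and placebo, and q the share of stoppers who reached 2 first, the same in both arms. Then

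completer difference = (0.3 - d1·q)/(1 - d1) - (0.3 - d0·q)/(1 - d0).

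- d1 = 30%, d0 = 10%, q = 0: 0.3/0.7 - 0.3/0.9 = 42.9% - 33.3% = +9.5 points.
- Same stopping, q = 50%: 0.15/0.7 - 0.25/0.9 = 21.4% - 27.8% = -6.3 points.

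| Stopping (elagolix vs placebo) | q = 0 | q = 30% | q = 50% |
|---|---|---|---|
| 30% vs 10% | +9.5 | 0 | -6.3 |
| 20% vs 10% | +4.2 | 0 | -2.8 |
| 15% vs 10% | +2.0 | 0 | -1.3 |

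In whole subjects, start from 6/20 and 9/30 with 6 and 3 stoppers. If no stopper had reached 2, completers are 6/14 vs 9/27, or +9.5 points. If 3 of the 6 and 1 of the 3 had, completers are 3/14 vs 8/27 = 21.4% vs 29.6%, or -8.2 points.

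Simulated rejection of the CMH at 0.1 (four strata of about equal size, 10,000 trials, q = 0) is about 16% for completers at 30% vs 10% stopping, about 12% at 20% vs 10%, and about 10% at 15% vs 10%. With all subjects kept it is about 10% throughout.

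**4. The same check against the proposed remedy**

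Now suppose instead that 30% in both arms would reach 2 under full exposure and that stopping is unrelated to ovulation. Let h be the share of would-be successes among stoppers who get there before stopping. The composite rate in an arm with stopping share d is 0.3·((1 - d) + d·h).

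- 30% vs 10%, h = 0: 21.0% vs 27.0%, -6.0 points.
- 30% vs 10%, h = 50%: 25.5% vs 28.5%, -3.0 points.
- 20% vs 10%: -3.0 points (h = 0) and -1.5 points (h = 50%).

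Here the completers-only difference is 0. At 30% vs 10% and h = 0 the composite rejects in about 13% of simulated trials and completers-only in about 10%. Each analysis is distorted where the other is sound.

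**The case against.** The exclusion in 8.5.4 is explicit and specific to the endpoint. A reader might infer that the SAP contradicts its own FAS rule and that the analysis is therefore invalid. The documents do not require that reading: the sentence can stand as a deliberate exception to a general rule. What survives is that the exception leaves this one proportion without a companion.

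A reader might also infer that the ovulation hypothesis is tested only in completers. It is not. The per-month analysis states no exclusion, so it appears to keep discontinuers, and it allows for exposure. It does not, however, answer the proportion endpoint.

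The strongest objection concerns the target. The 16% is a false-positive rate only if the quantity of interest is success before stopping. If the interest is in full exposure and stopping is unrelated to ovulation, a 42.9% versus 33.3% gap among completers would be a real effect, and it is the composite that would mislead. The SAP states no estimand for this endpoint. This objection stands, and it rules out the stronger claim that the composite must replace the completer analysis as the main one. The parallel with 8.5.1 is also loose: complete response requires maintenance to Month 6, whereas 2 ovulations can occur before stopping.

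Finally, 8.5.4 does not say whether it means stopping study drug or leaving the study. SAP 5.0 tabulates the two separately, and Protocol 5.6 keeps following subjects who stop drug. If study discontinuation is meant, fewer subjects are excluded and the illustrations above overstate the loss.

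**Conclusion.** The point holds as a gap in the planned analyses: the proportion with at least 2 ovulations is the only one of the four affected endpoints with no analysis that retains discontinuers. The possible distortion is about +9.5 to -6.3 points at 30% versus 10% stopping and no more than about 2 points at 15% versus 10%. It vanishes if stopping is equal (with the same q in both arms), or if stoppers succeed as often as completers. These figures rest on assumed stopping and ovulation rates and on the composite as target, so they show what could happen and are not a forecast. The documents do not support saying that the planned result will be biased, or that it will favour elagolix.

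The consequence is limited. This is an additional endpoint in a proof-of-concept study that SAP 10.0 leaves without Type I error control, and the primary and key secondary analyses do not depend on it. It is a cheap improvement worth making.

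**What to change.** In SAP 8.5.4:

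1. Add an FAS analysis of the proportion with the same stratified CMH. A subject who stops study drug early counts as a success if she had at least 2 ovulations on progesterone draws up to stopping; otherwise she does not meet the endpoint.
2. Report it side by side with the completers-only CMH. Which of the two is labelled main is for the sponsor to choose and state in advance.
3. State whether premature discontinuation here means study drug or study, and say that the completers-only analysis is an intended exception to the FAS rule.

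The cost is two or three sentences and one derivation from weekly draws already scheduled, with no new data. The composite counts short exposure as failure, so the reported proportion may be lower and unequal stopping can shift it even when stopping is unrelated to ovulation. It also leaves out draws taken after stopping drug under Protocol 5.6, so it is an on-treatment measure and should be described as one.
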